MRI. Participants will begin with MRI in the morning after their 16-hour dopaminergic washout the night/evening prior. Self-reported total sleep time the night prior will be recorded. They will be free to re-initiate therapy after MRI is complete. The following imaging and angiography sequences will be completed. We will apply our previously-reported 3T methods (16-channel neurovascular coil) with the below 50 min protocol:

- Anatomical imaging. *T*₁-weighted (MPRAGE; spatial resolution=1.0x1.0x1.0mm³; 3D turbo-gradient-echo; TR/TE=8.2/3.7ms), and T₂-weighted (FLAIR; spatial resolution=0.9x1.1x3.0mm³; turbo-inversion-recovery; TR/TI/TE=11000/2800/120ms) imaging, and intracranial (spatial resolution = 0.5x0.8x1.4mm³; 3D gradient echo; TR/TE=23/3.5ms) and extracranial (spatial resolution=0.9x0.9x3.0mm³; 2D gradient echo; TR/TE=18.6/3.2ms) time-of-flight (TOF) MR angiography (MRA).
- Microvascular hemodynamic compliance. A single-shot gradient echo echo-planar-imaging (EPI) scan (TE=30 ms), multiband-factor=3, isotropic spatial resolution=2 mm, SENSE-factor=2.5, and TR=1s will be acquired with whole-brain coverage. The scan will utilize a hypercapnic normoxic (5% CO₂ / 21% O₂ / 74% N₂) stimulus. The stimulus will be administered through a tight-fitting non-rebreathing oxygen facemask from compressed gas cylinders (flow rate=12 L/min) with the following paradigm: 180s normocapnic normoxia / 90s hypercapnia repeated once, followed by 180s normocapnic normoxia. Heart and respiration rate, EtCO₂, and FiO₂ will be recorded.
- CSF flow. 2D-Qflow measurements will be performed in the cerebral aqueduct (Fig. 7). V_{enc}=12 cm/s, spatial resolution = 0.5x0.5x4 mm³, field-of-view = 200x200x4 mm³, and 30 frames per heart cycle. Scan durations vary with heart rate, but are generally 2-4 min. Reproducibility has been determined by repeating the flow measurements in six subjects (Fig. 7). Background correction will be performed with a method previously developed for quantification of blood flow velocity in small perforating arteries⁴.

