Patients will undergo an initial evaluation with [name], the Rock Steady Boxing instructor. Each class consists of 60 minutes of intense aerobic exercise. Of note, this class is specifically designed for patients with gait, balance, and motor symptoms common to Parkinson's disease. Individuals with symptoms that preclude safe participation are screened out as part of the program's routine initial evaluation. All components of the class are non-contact, and strictly aerobic in nature. They will receive 20 class credits (over two installments), as the program recommends attempting to attend roughly twice per week. As this is an observational study, participants will not be excluded based on their attendance, though this variable will be monitored to aid in analyses and interpretation. As noted above, a final physical evaluation will also be conducted on their last class.

Follow-up

PD cohort

Clinical and neuroimaging assessments will be conducted within 1 week of completion of the exercise program.

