1 STATISTICAL PLAN

1.1 AIM 1

Aim (1). To quantify the relationship between CNS lymphatic measures and beta-amyloid burden.

- Hypothesis (1A). Glymphatic flow and lymphatic collector velocity inversely correlate with beta amyloid measured from 18F-florbetapir PET in older adults with Parkinson's disease.
- Exploratory Hypothesis (1B). In Parkinson's subjects matched for age and sex, glymphatic flow and betaamyloid burden will be worse in patients with versus without mild cognitive impairment (MCI).

A.1.1 Experiment. We will enroll participants with idiopathic Parkinson's disease (n=32; age range=55- 80 years), equally distributed and matched for age and sex between groups with (n=16) and without (n=16) mild cognitive impairment. These populations provide a cohort to evaluate the potential relationship between glymphatic flow and beta-amyloid burden, given the elevated risk of beta-amyloid accumulation associated with both conditions. These patients will form a cohort to be assessed before and after a community-based exercise intervention. Participants will be recruited from Vanderbilt University Medical Center Neurology's Behavioral and Cognitive and Movement Disorder Clinics by Drs. [name] and [name]. Potential participants will undergo a neurological and neuropsychological examination to characterize their medical and neurobehavioral status. Patients will have medical and motor presentation indicated for the community-based exercise program. Those patients with clinically-defined MCI, will be without evidence of vascular cognitive impairment, primary mood disorder, Lewy body disease, or comorbid medical condition that could contribute to cognitive symptoms (e.g. pulmonary, hematologic, metabolic, or vitamin deficiency).

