Exploratory Hypothesis (2A). Exercise treatment will result in improved glymphatic functioning. Exploratory Hypothesis (2B). Exercise treatment will result in a reduction of cortical beta-amyloid uptake. Exploratory Hypothesis (2C). The degree of improvements in glymphatic functioning and cortical beta-amyloid uptake in response to exercise therapy will be more significant in MCI versus non-MCI participants. D.2.1 Experiment. We will enroll the patients from Aim (1) (A.1.) all of whom are undergoing community-based exercise intervention to treat symptoms of Parkinson's.

A.2.1.1. Exercise intervention procedure. Following baseline assessment, all patients will participate in a community-based kick boxing group exercise class designed for those living with Parkinson's called "Rock Steady Boxing." Patients will complete 12 consecutive, 90-minute, once-weekly classes, then undergo follow-up assessment. Treatment compliance will be monitored by the collaborating exercise trainer. All participants, regardless of degree of treatment compliance will receive follow-up assessment. *A.2.1.2. Imaging procedure.* PET and MRI methods as outlined in A.1.1.2. and A.1.1.3. will be performed.

A.2.2. Analysis and statistical plan. Our main hypotheses are that after 12 weeks of once-weekly exercise treatment for PD, glymphatic functioning (per DTI-ALPS) will improve and beta-amyloid burden (per PET) will decline. We expect that degree of treatment compliance standards will moderate these changes. We will also explore whether scalar degree of treatment compliance relates to degree of change in our assessment modalities. Statistical analysis will be overseen by statistics Co-I [name] and the same considerations outlined in Aims (1) will be applied. To test Exploratory Hypothesis (2A), a paired Student's t-test or Wilcoxon signed-rank test, depending on normality findings, will be applied to determine if glymphatic flow (DTI-ALPS score) is increased after, relative to before, exercise intervention. To test Exploratory Hypothesis (2B), an identical

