procedure will be applied to evaluate differences in SUVr pre vs. post exercise intervention and corrected pvalues will be reported. To gain additional information, a multiple linear regression will be performed using the change in glymphatic flow (DTI-ALPS score) as the dependent variable and degree of compliance and change in beta-amyloid burden as the independent variables. To test Exploratory Hypothesis (2C), we will perform these same comparisons separately for MCI and non-MCI subgroups. Aim 2 hypotheses are exploratory, given limited extant literature defining reliable effect sizes; however, one randomized study (n = 33) demonstrated a 30% divergence in mean plasma levels of a CSF beta-amyloid marker between exercise (-6%) and non-exercise participants (+24%) with MCI. Thus, with the proposed sample size of 32 (each with a measurement before and after intervention), we should have at least 80% power to detect a significant difference in mean DTI-ALPS score pre- vs. post-exercise with at least 80% power and two-sided Type I error=5%. We should also have sufficient power to include two independent variables in the regression model. *A.2.3. Impact.* Results will provide evidence of how CNS lymphatic and beta-amyloid properties adjust in response to regular vigorous exercise in a PD sample.

A.3. Aim (3). Evaluate the degree to which neuroimaging-based response to exercise mediates clinical improvement in neurocognitive functioning and neuropsychiatric symptomatology.

Hypothesis 3.A. Neurocognitive functioning will improve following completion of the exercise intervention. Exploratory Hypothesis (3.B.). Sleep disturbance symptoms will diminish following completion of the exercise intervention.

Exploratory Hypothesis (3.C.). The degree of change glymphatic function and cortical beta-amyloid uptake in response to exercise therapy will be correlated with the degree of improvements in neurocognitive functioning.

Exploratory Hypothesis (3.D.). The degree of change glymphatic function and cortical beta-amyloid uptake in response to exercise therapy will be correlated with the degree of improvements in sleep disturbance symptomatology.

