Patient heterogeneity is a concern. Since other clinical factors can affect brain and cognitive functioning, we plan to control for age and screen for the most common medical conditions that might disproportionally affect outcome assessments. Furthermore, we have selected an age-cutoff that reduces clinical heterogeneity and has extant support for the presence of our conditions-of-interest. Patient recruitment. Vanderbilt University Medical Center's Neurology division has a large clinical volume of adult patients with Parkinson's. Thus, our recruitment target is felt to be reasonable. Patient attrition. We have accounted for a possible 10% attrition/exclusion in our protocol. We will use compliance as a scalar variable, allowing us to retain all patients at follow up, regardless of degree of compliance.

C. Sex as a biological variable. Given the relative infancy of the field of human CNS lymphatic imaging, to our knowledge there is no literature reporting sex differences for all proposed biomarkers of the lymphatic drainage system. Therefore, we have powered our study to specifically address this concern, and subjects will be recruited equally for both sexes and statistical measures are in place to evaluate how each observable varies with biological sex. This should be the first study to report how these properties of the lymphatic system differ with biological sex in humans.

D. Scientific rigor and reproducibility. The need to understand CNS small blood and lymphatic vessels is becoming increasingly recognized, with more than 150 manuscripts published in the last five years on this topic. However, nearly all studies utilize animal models only, and there is much less information available on how this system operates in humans in health or in the presence of clearance disorders such as Alzheimer's disease. One reason for this is that reliable methods for evaluating lymphatics in vivo are underdeveloped. Methods proposed here (e.g., CVR compliance, lymphangiography, glymphatic flow, and CSF flow velocity)

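### The attendance-change analyses in Aims 2 and 3 do not adjust for baseline motor severity or the baseline value of the outcome, so the attendance slope can be biased in either direction

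*SAP*

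**What the plan says.** The design is a single group of Parkinson's patients who all exercise (SAP A.1.1): "These patients will form a cohort to be assessed before and after a community-based exercise intervention". The healthy cohort completes only the time-estimation test and is no comparator for exercise.

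The one compliance model that is written out is in SAP A.2.2. Change in DTI-ALPS is the dependent variable, with "degree of compliance and change in beta-amyloid burden as the independent variables". The SAP adds: "We should also have sufficient power to include two independent variables in the regression model". It gives no effect size for that statement. A second, looser analysis appears in both A.2.2 and A.3.2: "We will also explore whether scalar degree of treatment compliance relates to degree of change in our assessment modalities". No method or covariate is named for it.

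Attendance is left to the participant. Protocol 2.2 (Exercise) says "participants will not be excluded based on their attendance, though this variable will be monitored to aid in analyses and interpretation", and SAP section B says "We will use compliance as a scalar variable, allowing us to retain all patients at follow up, regardless of degree of compliance". Protocol 2.3 counts a participant as a completer after a single class if both assessments are done, so the attendance range may be wide.

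Two statements bear on adjustment. SAP section B says, of patient heterogeneity, "we plan to control for age". A.2.2 repeats the Aim 2 comparisons within the MCI and non-MCI groups. Off-drug UPDRS-III is measured at baseline (Protocol 2.2 and Schedule of Activities), but no analysis in the SAP uses it as a covariate.

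**The concern.** With no control arm, attendance is the only contrast in exercise exposure that the trial has. A.2.2 expects compliance to moderate the changes, so the slope is of interest to the investigators.

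Patients choose how often they attend. The protocol itself links disease state to participation: it screens out people whose symptoms make the class unsafe (2.2) and lists disease progression as a reason for withdrawal (3.1). If severity at entry is related both to attendance and to change over 12 weeks, a regression without severity gives attendance a slope even when exercise does nothing. The baseline value of the outcome raises the same problem, because people who start low may change differently from people who start high. What is at stake is whether an attendance gradient, or its absence, can be interpreted at all.

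**Working it through.** **Reproducing the plan's figure.** A.2.2 gives no inputs for its two-predictor power statement, so that cannot be reproduced. The checkable figure is in A.1.3: 82% power for a correlation of -0.49 at n=32, two-sided 5%. By Fisher's z, atanh(0.49) × √29 = 0.536 × 5.385 = 2.887, and Φ(2.887 − 1.96) = 82.3%. It reproduces.

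**Inputs.** n=32 (SAP A.1.1) and n=50 (Protocol 2.1); two-sided alpha 5%. Let severity have correlation −a with attendance and −b with change in DTI-ALPS, and let the true exercise effect be zero. The documents give neither a nor b, so both are assumptions.

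**Size of the spurious association.** If severity is the only link between attendance and change, their correlation is (−a)(−b) = ab:
- a=0.3, b=0.3: 0.09
- a=0.5, b=0.3: 0.15

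**False-positive rate.** With δ = atanh(ab) × √(n−3), the two-sided rejection rate is about Φ(δ − 1.96) + Φ(−δ − 1.96).

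| a, b | n | δ | Fisher z | Simulation, attendance alone | Simulation, SAP's two predictors | Two predictors plus severity |
|---|---|---|---|---|---|---|
| 0.3, 0.3 | 32 | 0.486 | 7.0 + 0.7 = 7.7% | 8.1% | 7.4% | 5.1% |
| 0.5, 0.3 | 32 | 0.814 | 12.6 + 0.3 = 12.9% | 12.8% | 12.5% | 5.1% |
| 0.3, 0.3 | 50 | 0.619 | 9.0 + 0.5 = 9.5% | 9.4% | 9.1% | 5.1% |
| 0.5, 0.3 | 50 | 1.036 | 17.8 + 0.1 = 17.9% | 18.1% | 18.0% | 5.1% |

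Each simulated cell has 20,000 datasets. The bias does not shrink with sample size. It is detected more often at n=50, so the false-positive rate is higher there. The last column assumes that severity is measured without error.

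**Opposite direction.** If sicker patients attend less (correlation −0.5) but improve more (correlation +0.3), for example through regression to the mean, the spurious slope is −0.5 × 0.3 = −0.15 SD. In the simulation, significant results favouring attendance fall to 0.4% at n=32 and 0.2% at n=50, against a nominal 2.5%. A true slope of +0.15 SD would be cancelled (0.15 − 0.15 = 0).

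**Would controlling for age be enough?** With an age-like covariate correlated 0.3 with severity (assumed) added in place of severity, the two-sided rates are still 7.3% and 11.5% at n=32, and 8.7% and 15.5% at n=50.

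**Cost of adjusting.** For one coefficient among p predictors, take noncentrality f² × (n − p + 1) on 1 and n − p − 1 degrees of freedom, at 80% power. At n=32 the detectable partial f² is 0.271 for p=2 (0.271 × 31 = 8.4) and 0.303 for p=5 (0.303 × 28 = 8.5). Correlation between attendance and severity adds to this. At unchanged residual variance the standard error is multiplied by 1/√(1 − a²), which is 1/√0.91 = 1.05 for a=0.3 and 1/√0.75 = 1.15 for a=0.5.

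**The case against.** The strongest reply has four parts.

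- **Some adjustment is planned.** A reader might infer from the two-predictor model that the SAP ignores baseline covariates altogether. It does not: section B intends to control for age, the MCI groups are matched for age and sex, and the MCI subgroup repeat arguably extends to the regression. This stands. None of it is written into the compliance model, however, and none covers motor severity or the baseline outcome.
- **The direction is unknown.** A reader might infer that attendance will look falsely beneficial. Nothing in the documents says that severity drives a 12-week decline in DTI-ALPS, and the opposite sign is possible. This also stands, but a slope of uncertain bias is no easier to interpret.
- **The correlations may be small.** Enrolment requires a motor presentation suited to the programme, and unsafe participants are screened out, which narrows the severity range. At -0.3/-0.3 the inflation is modest, and that is a fair limit on the size of the point.
- **The analysis is exploratory.** A.2.2 labels the Aim 2 hypotheses so and offers the regression as additional information. No text says that the slope will be used to attribute change to exercise. The paired tests for 2A and 2B do not use compliance and are untouched. This lowers the consequence but leaves the bias in place.

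A further inference is tempting. Protocol 2.2 states "Self-reported total sleep time the night prior will be recorded", and no DTI-ALPS analysis uses that variable, so one might argue that sleep before the scan contaminates the DTI-ALPS change. The documents do not support this. Hypotheses 3B and 3D concern PROMIS sleep symptoms, not sleep duration before the scan. Sleep may also lie on the path from exercise to glymphatic change, in which case adjustment would remove part of the effect. No sleep adjustment is proposed here.

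**Conclusion.** The point holds for the compliance analyses only. As written, the attendance slope in A.2.2 and the looser compliance-change analyses in A.2.2 and A.3.2 are open to confounding by baseline motor severity and by the baseline outcome, although both are measured.

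Under the assumed correlations, a nominal 5% test with no exercise effect rejects about 8-13% of the time at n=32 and 9-18% at n=50. With the sign of the severity-change relation reversed, a real attendance effect could be masked. These rates rest on assumed correlations, on linear relations, and on severity being the only common cause. Weaker links would give less inflation.

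It is worth correcting before analysis because the remedy is cheap and because choosing covariates afterwards would raise its own doubts. It gives no ground for saying that the plan lacks covariates entirely, that the bias must favour exercise, or that the pre-post comparisons are invalid.

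**What to change.** 1. In A.2.2 and A.3.2, write the attendance model out: change in outcome on attendance, baseline value of that outcome, baseline off-drug UPDRS-III, age and MCI group. State that this is where section B's intention to control for age applies.
2. Report the adjusted attendance coefficient with its confidence interval beside the unadjusted one, and label both associational. Adjustment removes confounding only by what is measured, and UPDRS-III carries measurement error.
3. Keep the SAP's regression with change in SUVr as a separate analysis. Change in SUVr is measured after exercise, so the attendance coefficient in that model is not a total effect even with baseline adjustment.
4. Reconcile the passages that define attendance. SAP A.2.1.1 has 12 once-weekly 90-minute classes; Protocol 2.2 has 20 class credits for 60-minute classes at roughly two per week. Protocol 3.1, which allows withdrawal for significant non-compliance, must also be reconciled with SAP section B, which retains everyone. State which attendance measure enters the model once this is settled.

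The cost is SAP wording and three more predictors than the SAP's two. At n=32 the detectable partial f² rises from 0.271 to about 0.30, and the standard error widens further if attendance and severity are correlated. No new data are needed.

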1 PROTOCOL SUMMARY

1.1 SYNOPSIS

Title: Effects of Exercise on Glymphatic Functioning and Neurobehavioral

Correlates in Parkinson's Disease

Study Description: This study will assess patients with a clinical diagnosis of Parkinson's

disease (PD) over prior and following participation in a 12-week community-based exercise program, assessing neuroimaging (beta-amyloid deposition, glymphatic flow), and clinical severity (motor,

cognitive, sleep disturbance, mood).

Objectives: Primary Objective:

Evaluate the glymphatic functioning and beta-amyloid burden response to

12 weeks of a community-based exercise course in PD patients.

Secondary Objectives:

Quantify the association between glymphatic functioning, beta-amyloid

burden, and neurobehavioral dysfunction in PD.

Evaluate the degree to which neuroimaging-based response to exercise

mediates clinical improvement in PD.

Tertiary Objectives:

Evaluate whether the association between glymphatic functioning, betaamyloid burden, and neurobehavioral dysfunction in PD differs between

cognitively healthy and cognitively impaired PD phenotypes.

Evaluate whether the neuroimaging and clinical response to exercise differs between cognitively healthy and cognitively impaired PD

phenotypes.

Quaternary Objectives:

Develop a normative reference group for the Brief Estimate of Seconds Test (BEST) to facilitate PD score interpretation and establish how PD-related neurodegeneration affects time perception. In addition, determine how BEST scores correlate with disease severity, neuroanatomical ROIs, and neuropsychometric cognitive data collected in the previous objectives.

Endpoints: Primary Endpoints:

Glymphatic flow (DTI-ALPS score)
PET/CT (cortical:cerebellar SUVr ratio)

Secondary Endpoints (also used for Tertiary Endpoints):
Unified Parkinson's Disease Rating Scale III (UPDRS-3)

Actigraphy Mini-BEST-est

Freezing Gait Questionnaire

6-minute Walk Tesdt

Hopkins Verbal Learning Test-Revised (HVLT)

Trail Making Test – A & B (TMT)

Stroop Test (Stroop)

Letter Fluency (FAS) Simon Task (Simon)

PROMIS – Sleep Disturbance short forms (PROMIS-Sleep)

Hospital Anxiety and Depression Scale (HADS)

Tertiary Endpoints:

Clinical Dementia Rating Scale (CDR) Brief Estimate of Seconds Test (BEST)

Quaternary Endpoints:

Brief Estimate of Seconds Test (BEST)

Study Population: PD cohort: Patients with a clinical diagnosis of Parkinson's, as defined by

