2 STUDY DESIGN

2.1 OVERALL DESIGN

For the PD cohort, participants will be recruited from Vanderbilt University Medical Center Neurology's Behavioral and Cognitive and Movement Disorder Clinics by Drs. [name] and [name]. We will prospectively enroll participants with idiopathic Parkinson's disease (n=50; age range=55-80 years), equally distributed and matched for age and sex between groups with (n=25) and without (n=25) mild

cognitive impairment. These populations provide a cohort to evaluate the potential relationship between glymphatic flow and beta-amyloid burden, given the elevated risk of beta-amyloid accumulation associated with PD and MCI conditions. Patients will have medical and motor presentation indicated for the community-based exercise program. Those patients with clinically-defined MCI, will be without evidence of vascular cognitive impairment, primary mood disorder, or comorbid medical condition that could contribute to cognitive symptoms (e.g. pulmonary, hematologic, metabolic, or vitamin deficiency). Potential participants will undergo a neurological and neuropsychological examination (including cognitive exam and behavioral/symptom questionnaires) to characterize their medical and neurobehavioral status. They will then undergo baseline neuroimaging protocols, both MRI brain scan (DTI-ALPS) and PET/CT (C11PiB) brain scan. Actigraph will be attached to the patient to continuously monitor motor activity. A background monitor of typing cadence will be activated on their computer to monitor for changes in fine motor control. The cohort will complete the same clinical and neuroimaging assessments after they participate in a 12-week community-based exercise intervention. Specifics about assessments and the exercise program are as follows.

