A.1.3. Statistical concerns. Statistical analyses will be overseen by statistician Co-I [name]. Descriptive statistics, including means, standard deviations, and ranges for continuous parameters, as well as percent and frequency for categorical parameters, will be presented. Tests for normality and homoscedasticity will be made. To test Hypothesis (1A), Pearson or Spearman (depending on normality findings) will be applied to evaluate the relationship between glymphatic flow, measured as the DTIALPS score, and the cortical:cerebellar SUVr, measured from PET. As an exploratory analysis to understand whether the relationship is spatially dependent, correlation testing will be repeated using the regional SUVr measures and corrected p-values reported. Power calculations are based on preliminary data in six MCI subjects in which an inverse correlation (Spearman's alpha =-0.49) was found between SUVr and DTI-ALPS score. With a sample size of 32, we should have 82% power to detect a correlation of -0.49 with two-sided p<0.05. To test Exploratory Hypothesis (1B), we will apply a Student's t-test or Wilcoxon rank-sum test (depending on normality findings), to evaluate whether mean glymphatic flow, measured as the DTI-ALPS score, is different between age- and sex-matched participants with vs. without MCI. Motivation is based on our preliminary data, where we have observed a large effect size (Cohen's d=2.3) in DTI-ALPS score between age- and sex-matched subjects with vs. without MCI.

A.1.4. Impact. Results will for the first time evaluate how the proposed human CNS lymphatic system and levels of beta-amyloid burden are altered in Parkinson's disease. If confirmed, results will motivate the use of evaluating human CNS lymphatic dysfunction with proposed methods for understanding betaamyloid clearance disorders.

A.2. Aims (2). Quantify the glymphatic functioning and beta-amyloid burden response to 12 weeks of a community-based exercise course developed specifically for PD patients.

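### Hypothesis 2C asks whether imaging response to exercise is greater in MCI than non-MCI, but the plan only tests pre/post change within each subgroup and never compares the changes

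*SAP*

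**What the plan says.** SAP Aim 2, Exploratory Hypothesis 2C, states that improvement in glymphatic functioning and cortical amyloid uptake "will be more significant in MCI versus non-MCI participants". The protocol asks the same in its tertiary objectives (1.1 Synopsis): "Evaluate whether the neuroimaging and clinical response to exercise differs between cognitively healthy and cognitively impaired PD" phenotypes. The protocol gives no analysis for that objective.

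SAP A.2.2 gives one analysis for 2C: "we will perform these same comparisons separately for MCI and non-MCI subgroups". The comparisons meant are those of 2A and 2B just before it: a paired t-test or Wilcoxon signed-rank test of follow-up against baseline, for DTI-ALPS and for SUVr.

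Group sizes differ between the documents. SAP A.1.1 splits the sample "between groups with (n=16) and without (n=16) mild cognitive impairment". Protocol 2.1 has the cohort "equally distributed and matched for age and sex between groups with (n=25) and without (n=25) mild" cognitive impairment. Both sizes are carried through below.

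**The concern.** A paired test within a subgroup asks whether that subgroup's mean change differs from zero. Hypothesis 2C asks whether two mean changes differ from each other. Two within-group p-values do not answer this: one group can reach significance and the other miss it when the true changes are the same, and both can reach significance when the changes differ.

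The SAP does not say what pattern of subgroup results would count for or against 2C, and it plans no difference in change with an interval. The likely outcome is an informal reading of the two p-values. A claim that cognitively impaired patients respond more to exercise could then rest on chance differences in significance.

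**Working it through.** **1. Does any other analysis supply the contrast?**

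- Hypothesis 1B (SAP A.1.3) does compare the groups, testing whether mean DTI-ALPS "is different between age- and sex-matched participants with vs. without MCI". That is the level of the score, not its change.
- The Aim 2 regression (A.2.2) models change in DTI-ALPS, with "degree of compliance and change in beta-amyloid burden as the independent variables". It has no MCI term. Fitting it separately by subgroup would still give no contrast.
- A.2.2 carries over the considerations of Aim 1. These cover descriptive statistics, assumption checks and the tests for 1A and 1B; none concerns a difference in change.

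Neither document contains an interaction, a group-by-time term or a change-score comparison.

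**2. The plan's own figures.** No power figure is given for 2C. The 80% in A.2.2 is for the whole-sample pre/post DTI-ALPS comparison and comes with no effect size or SD of change, so it cannot be reproduced. Solving a paired t-test for 80% power at n=32, two-sided 5%, gives dz = 0.51 (mean change divided by SD of change).

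**3. Illustration of what separate tests can do.** Assumptions: significant improvement in MCI and a non-significant result in non-MCI is read as support for 2C; the true standardized change dz is the same in both groups; tests are two-sided at 5%.

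For a paired t-test with n participants, power p comes from the noncentral t with n − 1 degrees of freedom and noncentrality dz × √n. Let u be the part of p in the direction of improvement. The groups are independent, so

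P(false support) = u(MCI) × [1 − p(non-MCI)].

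At dz = 0.5, u and p agree to three decimals:

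- n = 16: 0.465 × (1 − 0.465) = 0.249
- n = 25: 0.670 × (1 − 0.670) = 0.221

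The rate depends strongly on the assumed dz:

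| dz in both groups | 16 per group | 25 per group |
|---|---|---|
| 0 | 2.4% | 2.4% |
| 0.3 | 16.1% | 21.1% |
| 0.5 | 24.9% | 22.1% |
| 0.7 | 19.0% | 7.5% |
| 1.0 | 3.7% | 0.2% |

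With equal groups the product peaks at 25%, but that is not a general ceiling. At dz = 0.5 with 16 MCI and 14 non-MCI completers it is 0.465 × (1 − 0.410) = 0.274; with 25 and 22 it is 0.262. With the same raw mean change (0.5 SD of MCI change) but an SD of change 1.25 times larger in non-MCI, it is 31.5% at 16 per group and 34.6% at 25. With that SD 0.8 times as large, it is 16.4% and 10.0%.

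A direct two-sample t-test on change has a 2.5% error rate in the MCI-favouring direction. Simulation (200,000 runs, dz = 0.5) gave 0.025 for the direct test, and 0.248 (16 per group) and 0.221 (25 per group) for the subgroup reading.

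**4. What a direct comparison can deliver.** For n per group, the noncentrality is d / √(2/n) with 2n − 2 degrees of freedom, where d is the difference in mean change in SDs of change. The 95% CI half-width is t(0.975, 2n − 2) × √(2/n).

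- n = 16: 2.042 × √(2/16) = 0.72 SD
- n = 25: 2.011 × √(2/25) = 0.57 SD

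| Per group | Detectable d, 80% power, alpha 0.05 | Same, alpha 0.025 |
|---|---|---|
| 16 | 1.02 | 1.14 |
| 14 | 1.10 | 1.23 |
| 25 | 0.81 | 0.90 |
| 22 | 0.86 | 0.96 |

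The rows for 14 and 22 assume that 10% attrition comes off the stated sizes (16 × 0.9 = 14.4; 25 × 0.9 = 22.5). The alpha 0.025 column assumes that the corrected p-values mentioned in A.2.2 mean a split over the two imaging endpoints. Power for d = 0.5 at alpha 0.05 is 28% at 16 per group and 41% at 25.

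**The case against.** The strongest reply is that 2C is labelled exploratory, nothing primary rests on it, and the direct comparison has low power. This limits the severity. It does not rescue the analysis: the SAP still presents the subgroup tests as the test of 2C, and the question is a named tertiary objective. Low power is a reason to report an estimate with its interval, not two p-values that address another question.

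A second reply is that subgroup means before and after will probably be tabulated, so a reader could subtract the changes. That is true of the point estimate. A standard error for the difference cannot be recovered from pre and post means and SDs alone, and no interval is planned.

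Third, the error rates rest on a decision rule that the SAP does not state, and 0.5 is close to the worst case at 16 per group. Both points stand, so the rates are illustrations. They are also per endpoint, whereas 2C names both. At dz = 0.5 with independent changes, requiring the pattern on both endpoints gives 0.249² = 6% (16 per group) or 0.221² = 5% (25 per group). Accepting it on either gives 1 − 0.751² = 44% or 1 − 0.779² = 39%.

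Fourth, SAP section B says 10% attrition has been allowed for, without saying whether 32 is before or after losses. The figures for 14 and 22 per group are therefore a sensitivity range.

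Finally, A.1.3 reports a large preliminary DTI-ALPS difference between subjects with and without MCI (Cohen's d = 2.3). If the groups start far apart, a comparison of raw change depends on the measurement scale. That is a caveat for interpreting the contrast; separate subgroup tests do not remove it.

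**Conclusion.** The concern holds. Following the SAP exactly would neither test nor estimate the difference in response that 2C and the imaging part of the tertiary objective ask about. This rests on the text alone and needs no assumed effect size.

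How far a reader might be misled depends on assumptions the documents do not settle: the decision rule, the true change, the SDs of change and the number of completers. With equal groups and equal SDs, the per-endpoint chance of apparent support without a true difference runs from about 0.2% to 25% over dz from 0 to 1.0. It can exceed that range with unequal completers or unequal SDs. A direct test holds 2.5% in the same direction. The point should be fixed before analysis; because 2C is exploratory, the primary endpoints and the sample size are unaffected.

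**What to change.** Replace the 2C sentence in SAP A.2.2 with a direct comparison:

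- Compute change (follow-up minus baseline) in DTI-ALPS and SUVr for each participant and compare MCI with non-MCI by a two-sample t-test. The equal-variance form is equivalent to the group-by-time interaction. A.1.3 already says "Tests for normality and homoscedasticity will be made", so name the Welch form for unequal variances, or simply use Welch throughout, and a rank-sum test on change for non-normal data.
- Report the difference in mean change with a 95% CI. If the rank-sum test is used, add a matching interval such as Hodges–Lehmann.
- Keep the within-subgroup pre/post tests as descriptive.
- State the precision openly: 80% power only for about 1.02 SD of change at 16 per group or 0.81 SD at 25, with CI half-widths of 0.72 and 0.57 SD. Say whether the p-value correction covers the two endpoints.
- If the contrast is extended to clinical endpoints under the tertiary objective, label it descriptive. For the memory and executive scores, add that they define MCI at baseline (A.1.1.1, A.1.2.1) and are also outcomes (A.3.2). Regression to the mean can therefore produce apparent greater improvement in the MCI group.

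The cost is a few SAP sentences, with no new data, visits or participants. The downside is a published power of about 28% (16 per group) or 41% (25 per group) for a 0.5 SD difference. The gain is an honest estimate with its uncertainty, not a decisive test.
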